6.3.5. Pharmacokinetics

As many of the specific PK samples should be obtained from each participant as is feasible.

- Cohorts 1-2: samples collected on CCI [REDACTED]
 - Day 3: 1 sample between CCI [REDACTED]
 - Day 5: predose CCI [REDACTED] and at CCI [REDACTED] postdose
 - Day 5: CCI [REDACTED] postdose for hospitalized participants only

The PK sample collection timepoints for Cohorts 3-7 will be provided in a protocol amendment.

6.3.6. Clinical Virology

6.3.6.1. Virology Testing

6.3.6.1.1. Virology Samples to Address the Study Objectives

Midturbinate nasal swab samples will be used to assess SARS-CoV-2 viral load by reverse transcription-quantitative PCR at the time points specified in [Table 1](#). Once viral load testing is complete, the remnant samples may be used to evaluate SARS-CoV-2 viral titer, emergence of viral resistance (by SARS-CoV-2 sequencing and/or phenotypic testing), and viral coinfection.

6.3.6.1.2. Virology Sample Storage

Any remaining specimens from midturbinate nasal swab samples collected during the study will be stored and retained for possible future virology-related testing. These stored samples may be used by the sponsor or its research partners for viral genotyping/phenotyping assays or their development, for retesting the amount of virus present in the sample, or for testing to learn more about how the study drug has worked or clinical laboratory testing to provide additional safety data. At the conclusion of this study, these samples may be retained in storage by Gilead for a period up to 15 years or per country requirements.

6.3.7. Participant Symptom Assessment

Participant and/or parent/caregiver will complete participant symptom assessment daily from Day 1 through Day 14 and at Days 21, 28, and 35 via a symptom score questionnaire.

The questionnaire will consist of severity (on 4- or 5-point scale, as applicable) of select symptoms (listed below), frequency of select symptoms (diarrhea and vomiting) in 24 hours before the assessment, and smell and taste assessment.

The select symptoms for severity assessment on 4- or 5-point scale will include:

- Stuffy or runny nose
- Sore throat
- Shortness of breath
- Cough
- Low energy or tiredness
- Muscle or body aches
- Headache
- Chills or shivering

- Feeling hot or feverish
- Nausea

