2. OBJECTIVES AND ENDPOINTS

Primary Objectives	Primary Endpoints

• To evaluate the plasma PK of ODV in pediatric participants with COVID-19• To evaluate the safety and tolerability of ODV in pediatric participants with COVID-19	
• PK parameters (AUC₀₋₁₂, C_{max}, and C_{trough}) for ODV metabolite, GS-441524• Incidence of treatment-emergent AEs by Day 35• Incidence of treatment-emergent laboratory abnormalities by Day 35
Secondary Objectives	Secondary Endpoints

• To assess the impact of ODV on time to sustained alleviation of targeted COVID-19 symptoms in pediatric participants with COVID-19• To evaluate the antiviral activity of ODV on SARS-CoV-2 nasal swab viral load in pediatric participants with COVID-19• To assess the impact of ODV on the requirement for supplemental oxygen in pediatric participants with COVID-19• To evaluate palatability and acceptability of ODV in pediatric participants with COVID-19• To provide data on the use of medications other than RDV and ODV for treatment of COVID-19 in pediatric participants with COVID-19• To assess the impact of ODV on COVID-19-related hospitalizations or all-cause death in pediatric participants with COVID-19	
• Time to sustained alleviation of targeted COVID-19 symptoms by Day 35• Change from baseline in SARS-CoV-2 nasal swab viral load at Day 5• Proportion of participants who require supplemental oxygen support (low flow oxygen, high flow oxygen, noninvasive ventilation, mechanical ventilation, or extracorporeal membrane oxygenation) by Day 35• Assessment of palatability and acceptability scores of each formulation at Day 5• Proportion of participants with concomitant use of medications other than RDV and ODV for treatment of COVID-19 by Day 35• Proportion of participants with COVID-19-related hospitalization or all-cause death by Day 35

CCI

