8.1.1. Secondary Endpoints

Additional information on the secondary endpoints listed in Section [2](#) is provided below.

- Time (days) to sustained alleviation of targeted COVID-19 symptoms by Day 35

This secondary efficacy endpoint will be assessed via the participant symptom assessment. Symptom alleviation is defined as follows: all targeted symptoms scored moderate or severe at baseline are scored as mild or none for at least 48 consecutive hours, and all targeted symptoms scored mild or none at baseline are scored as none for at least 48 consecutive hours; the first day of the 48 consecutive hours will be considered the symptom alleviation date. Details of the COVID-19 symptoms to be assessed are provided in Section [6.3.7](#).

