8.5.2. Secondary Analyses

The time to sustained alleviation of targeted COVID-19 symptoms by Day 35 is calculated as the symptom alleviation date minus the first dose date plus 1 day. In case, prior to data cutoff a participant:

- Completes the study without alleviation of targeted COVID-19 symptoms
- Discontinues from the study early prior to alleviation of targeted COVID-19 symptoms (due to AE, lack of efficacy, investigator's discretion, noncompliance with study drug, protocol violation, participant decision, lost to follow-up)

The time to sustained alleviation of targeted COVID-19 symptoms will be calculated as the last date on which the symptom alleviation is assessed by Day 35 minus the first dose date plus 1 day or Day 34, whichever occurs first.

In addition, if prior to data cutoff a participant:

- Dies from any cause prior to alleviation of targeted COVID-19 symptoms
- Takes rescue medication prior to alleviation of targeted COVID-19 symptoms

he/she will be regarded as not having the event of interest and will be censored at Day 34.

The timing to sustained alleviation of targeted COVID-19 symptoms will be estimated by cohort and overall using the Kaplan-Meier (KM) method. The median time to sustained alleviation of targeted COVID-19 symptoms along with the 95% CI will be presented. The proportion of participants with sustained alleviation of targeted COVID-19 symptoms using KM estimates will be provided in summary tables and plots by cohort and overall.

For continuous variables, data and change from baseline at all scheduled time points will be summarized by cohort and overall. For categorical variables, the number and percentage of participants in each category within a variable will be presented by cohort and overall.

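### The symptom endpoint runs to Day 35, but a 48-hour alleviation cannot be confirmed if it starts after about Day 13, because daily questionnaires stop at Day 14

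*Protocol*

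**What the plan says.** Four parts of the protocol bear on this endpoint.

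- **Horizon (section 2).** The secondary endpoint is "Time to sustained alleviation of targeted COVID-19 symptoms by Day 35".
- **Event (section 8.1.1).** Symptoms moderate or severe at baseline must be such that they "are scored as mild or none for at least 48 consecutive hours". In addition, "all targeted symptoms scored mild or none at baseline are scored as none for at least 48 consecutive hours". On dating, "the first day of the 48 consecutive hours will be considered the symptom alleviation date".
- **Data collection (section 6.3.7).** The participant or caregiver "will complete participant symptom assessment daily from Day 1 through Day 14 and at Days 21, 28, and 35".
- **Analysis (section 8.5.2).** A participant who completes or leaves the study without alleviation is given a time equal to the last assessment date by Day 35 "minus the first dose date plus 1 day or Day 34, whichever occurs first". Deaths and rescue-medication use before alleviation are censored at Day 34. The Kaplan-Meier median with its 95% confidence interval, and the Kaplan-Meier proportion alleviated, are reported by cohort and overall.

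Section 8.3.2 adds that missing values are in general not imputed. The protocol gives no rule for confirming a 48-hour run from records a week apart.

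**The concern.** The event needs consecutive daily information, and that information stops three weeks before the endpoint does. A Day 34 cap makes sense as the last possible start of a 48-hour run only if the questionnaire is daily through Day 35. Here, a participant still symptomatic in the second week stays in the risk set for up to three more weeks in which the event, as defined, cannot be shown to occur.

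This matters more than usual for a secondary endpoint because the study has a single arm. No control group shares the distortion, so the absolute proportion by cohort is itself the result. Section 8.2.1 also allows interim analyses to be submitted to regulators in support of extending the indication. Daily scores that were never collected cannot be recovered later.

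**Working it through.** **1. Last start that can be confirmed.** Scheduled records fall on Days 1 to 14, 21, 28 and 35. The protocol does not say how many daily records make up 48 hours, so both readings are shown.

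| Records needed | Last confirmable start | Days left to the Day 34 cap |
|---|---|---|
| 2 consecutive days | Day 13 (Days 13, 14) | 34 − 13 = 21 |
| 3 consecutive days | Day 12 (Days 12, 13, 14) | 34 − 12 = 22 |

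After Day 14 the gaps are 21 − 14, 28 − 21 and 35 − 28, each 7 days. No two scheduled records lie within 48 hours of each other. With daily records through Day 35, the last confirmable start would be Day 34 (two records) or Day 33 (three), which matches the cap.

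**2. What the Kaplan-Meier estimate then shows.** Let F(t) be the true proportion alleviated by day t. With no events possible after Day 13 and unresolved completers retained, the Day 34 estimate is about F(13), not F(34). The shortfall is F(34) − F(13).

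**3. Illustrative size (assumption).** The protocol states no expected alleviation time. Section 1.1 cites median illness durations of 5 days (ages 5 to 11) and 7 days (ages 12 to 17), and 4.4% lasting at least 28 days. Take these as a proxy for time from first dose and assume a log-normal form. The log-SD is σ = ln(28/median) / z(0.956), and F(t) = Φ(ln(t/median)/σ).

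| Median (days) | σ | F(13) | F(34) | F(34) − F(13) | F(34) − F(12) |
|---|---|---|---|---|---|
| 5 | 1.010 | 0.828 | 0.971 | 0.143 | 0.164 |
| 6 | 0.903 | 0.804 | 0.973 | 0.169 | 0.194 |
| 7 | 0.813 | 0.777 | 0.974 | 0.197 | 0.228 |

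On the two-record reading, 14-20% of participants alleviate in the period that cannot be confirmed. In a cohort of 12 that is 12 × 0.143 = 1.7 to 12 × 0.197 = 2.4 participants. The three-record reading gives 16-23%.

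**4. If a single weekly record is accepted instead.** The 48-hour rule is then unverified, and the event is dated to the next record. For true starts on Days 15 to 34 the delays are 6, 5, 4, 3, 2, 1, 0 (Days 15 to 21), the same again (Days 22 to 28), and 6, 5, 4, 3, 2, 1 (Days 29 to 34). They sum to 63 over 20 days, a mean of 3.15 days and a maximum of 6.

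**5. Visit windows.** If the Table 1 windows also govern the questionnaire, a Day 28 record at Day 30 and a Day 35 record at Day 30 could coincide (28 + 2 against 35 − 5). Two late records within 48 hours are therefore possible by accident, but the schedule does not plan for them.

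**The case against.** The strongest reply is that little depends on this. The primary endpoints are pharmacokinetic and safety, section 8.5 plans no formal efficacy testing, and section 8.5.1 says that there is no primary efficacy analysis. The median is one of the two reported summaries, and the only durations in the protocol put it well inside the daily window. Section 8 defers statistical detail to the analysis plan, which was not available here and could set a convention for the weekly records or use interval censoring. All of this stands and limits the seriousness. It does not remove the point: an analysis plan can choose between a flat curve and imprecise dates, but it cannot supply daily scores that were not collected.

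A reader might also infer more than the documents support:

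- **That nothing is recorded after Day 14.** Symptoms are recorded on Days 21, 28 and 35. What is lost is confirmation of the 48-hour run and its start date.
- **That every unresolved participant is at risk to Day 34.** Section 8.5.2 uses the last assessment when that is earlier, so early exits leave the risk set then. The statement fits completers assessed on Day 34 or later, and deaths and rescue use.
- **That the median cannot be estimated.** This would follow only if a cohort's median lay beyond about Day 13, and no figure in the protocol makes that likely.
- **That the rule for early exits is an error.** Section 8.5.2 covers a participant who "Discontinues from the study early prior to alleviation of targeted COVID-19 symptoms (due to AE, lack of efficacy" and censors at last assessment, whereas death and rescue go to Day 34. Censoring at last contact is a standard choice, stated openly. Preferring another is a choice of estimand. Section 6.4.1 also asks that participants who stop dosing be kept in follow-up, which should make such exits few.

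**Conclusion.** The event definition, the questionnaire schedule and the Day 35 horizon do not fit together. Starts after Day 13 (Day 12 on the stricter reading) cannot be confirmed on the planned schedule. That conclusion comes from the protocol's own rules and needs no distributional assumption.

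The size does need one. Under the log-normal illustration, the Day 34 proportion would read about 0.78-0.83 instead of about 0.97 if the definition is applied strictly. The cited illness durations are only a proxy: they are not measured from first dose and do not come from this at-risk population. Accepting weekly snapshots replaces that bias with unverified events dated up to about 6 days late. The damage is confined to the late part of the curve, and a median of 5 to 7 days is unaffected. The point should be corrected, but because the endpoint is secondary and descriptive it does not threaten the study's main conclusions.

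**What to change.** **Preferred.** In section 6.3.7 and Table 1, continue the same once-daily questionnaire after Day 14 for participants not yet alleviated, until a 48-hour alleviation is recorded or Day 35 is reached. State in section 8.1.1 whether 48 hours means two or three consecutive daily records. The cost is protocol wording, a diary setting and extra questionnaires for a minority. Under the illustration, 1 − F(13) is 17-22% of participants, or two to three in a cohort of 12. Each would complete at most 18 more (Days 15 to 35 are 21 days, of which 3 are already scheduled).

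**Otherwise.** Restate the endpoint as by Day 14 in the synopsis and in sections 2, 8.1.1 and 8.5.2. Censor unresolved participants at the last evaluable 48-hour start (Day 13 on the two-record reading), and move the Day 34 value for deaths and rescue use to the same day so that there is one horizon. Report Days 21, 28 and 35 only as the percentage alleviated on that day. This needs no new data, but gives up any time-to-event statement about late recovery.

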6.3.7.1. Procedures to Minimize Missing Symptom Data

To minimize missing symptom data, following steps are put in place to help participants remain compliant with questionnaire completion per protocol required time points:

- Participants may receive reminders/notifications on stipulated days ([Table 1](#)) to complete questionnaire.
- Site staff and the study monitor will review symptom questionnaire data completion reports to monitor compliance.
- Site staff will contact participants and/or parent/caregiver regarding missing data (or their close contact in case of nonresponse, where feasible).
- Participants and/or parent/caregiver may be provided with a Value Sheet (if available) to highlight the significance of symptom questionnaire data and importance of participant compliance for the purpose of this study.

6.3.8. Assessment of Palatability and Acceptability

To assess palatability and acceptability of study drug, the participant or parent/caregiver will rate acceptability and palatability of the applicable formulation using a 5-point facial recognition scale.

Parent/caregiver may answer additional questions regarding preparation and dosing of the age-appropriate formulation.

6.4. Assessments for Early Discontinuation From Study Intervention or From the Study

6.4.1. Assessments for Early Discontinuation From Study Intervention

If a participant discontinues study dosing prematurely (eg, as a result of an AE), every attempt should be made to keep the participant in the study and continue to perform the required study-related follow-up and procedures (see [Section 3.3](#)). If this is not possible or acceptable to the participant or investigator, the participant may be withdrawn from the study.

6.4.2. Assessments for End of Study

A participant who completes the study undergo end of study visit as specified in [Table 1](#).

6.5. Poststudy Care

The long-term care of the participant will remain the responsibility of their primary treating physician. There is no provision for poststudy availability.

6.6. Sample Storage

The stored biological samples may be used by Gilead or its research partner for additional testing to provide supplemental data to answer questions that relate to the main study. At the end of this study, these samples may be retained in storage by Gilead for a period up to 15 years or per country requirements.

7. ADVERSE EVENTS AND TOXICITY MANAGEMENT

7.1. Definitions of Adverse Events and Serious Adverse Events

7.1.1. Adverse Events

An AE is any untoward medical occurrence in a clinical study participant administered a study drug that does not necessarily have a causal relationship with the treatment. An AE can therefore be any unfavorable and/or unintended sign, symptom, or disease temporally associated with the use of a study drug, whether or not the AE is considered related to the study drug. Adverse events may also include pretreatment or posttreatment complications that occur as a result of protocol-specified procedures or special situations (Section 7.1.3).

An AE does not include the following:

- Medical or surgical procedures such as surgery, endoscopy, tooth extraction, or transfusion. The condition that led to the procedure may be an AE and must be reported.
- Preexisting diseases, conditions, or laboratory abnormalities present or detected before the screening visit that do not worsen.
- Situations where an untoward medical occurrence has not occurred (eg, hospitalization for elective surgery, social and/or convenience admissions).
- Overdose without clinical sequelae (Section 7.1.3).
- Any medical condition or clinically significant laboratory abnormality with an onset date before the ICF is signed and not related to a protocol-associated procedure is not an AE but rather considered to be preexisting and should be documented as medical history.

Preexisting events that increase in severity or change in nature after study drug initiation or during or as a consequence of participation in the clinical study will also be considered AEs.

7.1.2. Serious Adverse Events

An SAE is defined as an event that, at any dose, results in the following:

- Death.
- A life-threatening situation (Note: The term “life-threatening” in the definition of “serious” refers to an event in which the participant was at risk of death at the time of the event; it does not refer to an event that hypothetically might have caused death if it were more severe.)
- In-patient hospitalization or prolongation of existing hospitalization.

- Persistent or significant disability/incapacity.
- A congenital anomaly/birth defect.
- A medically important event or reaction: Such events may not be immediately life-threatening or result in death or hospitalization but may jeopardize the participant or may require intervention to prevent 1 of the other outcomes constituting SAEs. Medical and scientific judgment must be exercised to determine whether such an event is reportable under expedited reporting rules. Examples of medically important events include intensive treatment in an emergency room or at home for allergic bronchospasm; blood dyscrasias or convulsions that do not result in hospitalization; and development of drug dependency or drug abuse.

7.1.3. Study Drugs and Gilead Concomitant Medications Special Situations Reports

Special situations reports (SSRs) include all reports of medication error, abuse, misuse, overdose, occupational exposure, drug interactions, exposure via breastfeeding, unexpected benefit, transmission of infectious agents via the product, counterfeit of falsified medicine, and pregnancy regardless of an associated AE.

Medication error is any unintentional error in the prescribing, dispensing, preparation for administration or administration of a study drug while the medication is in the control of a health care professional, participant, or consumer. Medication errors may be classified as a medication error without an AE, which includes situations of missed dose, medication error with an AE, intercepted medication error, or potential medication error.

Abuse is defined as persistent or sporadic intentional excessive use of a study drug by a participant.

Misuse is defined as any intentional and inappropriate use of a study drug that is not in accordance with the protocol instructions or the local prescribing information.

An overdose is defined as an accidental or intentional administration of a quantity of a study drug given per administration or cumulatively that is above the maximum recommended dose as per protocol or in the product labeling (as it applies to the daily dose of the participant in question). In cases of a discrepancy in drug accountability, overdose will be established only when it is clear that the participant has taken the excess dose(s). Overdose cannot be established when the participant cannot account for the discrepancy, except in cases in which the investigator has reason to suspect that the participant has taken the additional dose(s).

Occupational exposure is defined as exposure to a study drug as a result of one's professional or nonprofessional occupation.

Drug interaction is defined as any drug/drug, drug/food, drug/alcohol, or drug/device interaction.

Unexpected benefit is defined as an unintended therapeutic effect where the results are judged to be desirable and beneficial.

Transmission of infectious agents is defined as any suspected transmission of an infected agent through a Gilead study drug.

Counterfeit or falsified medicine is defined as any study drug with a false representation of (a) its identity, (b) its source, or (c) its history.

7.2. Assessment of Adverse Events and Serious Adverse Events

The investigator or qualified subinvestigator is responsible for assessing AEs and SAEs for causality and severity, and for final review and confirmation of accuracy of event information and assessments.

7.2.1. Assessment of Causality for Study Drugs and Procedures

The investigator or qualified subinvestigator is responsible for assessing the relationship for each study drug using clinical judgment and the following considerations:

- **No:** Evidence exists that the AE has an etiology other than the study drug. For SAEs, an alternative causality must be provided (eg, preexisting condition, underlying disease, intercurrent illness, concomitant medication).
- **Yes:** There is reasonable possibility that the AE may have been caused by the study drug.

It should be emphasized that ineffective treatment should not be considered as causally related in the context of AE reporting.

The relationship to study procedures (eg, invasive procedures such as venipuncture or biopsy) should be assessed using the following considerations:

- **No:** Evidence exists that the AE has an etiology other than the study procedure.
- **Yes:** The AE occurred as a result of protocol procedures (eg, venipuncture).

